Protocol Summary Form

[name], PhD Candidate, Duquesne University School of Nursing

The Psychosocial and Physiological Effects of Teaching Mindfulness Based Stress Reduction (MBSR) to Adolescents with Type 1 Diabetes

Research Questions

Does a learned mindfulness based stress reduction program offered online increase mindfulness and improve quality of life in adolescents with Type 1 diabetes compared to a control group of adolescents with Type 1 diabetes?

Does a learned mindfulness based stress reduction program offered online result in the physiological benefit of reduced HbA1c measurements in adolescents with Type 1 diabetes compared to a control group of adolescents with Type 1 diabetes?

Purpose and significance of the study

The prevalence of Type 1 diabetes in Americans under age 20 rose by 23 percent between 2001 and 2009 (Juvenile Diabetes Research Foundation, 2011). The dependence of individuals with Type 1 diabetes on the self-administration of insulin and constant monitoring of blood glucose levels related to diet, exercise, health status, growth and sexual maturity make the management of this condition intensely demanding (Tilden, Charman, Sharples, & Fosbury, 2005). The fact that Type 1 diabetes strikes most often in childhood also has significant implications for disease management. Considerable stress is associated in adolescents with Type 1 diabetes (Watts, O'Hara, & Trigg, 2010). It is imperative that nurses and other health care professionals find ways by which stress can be reduced in the service of improving quality of life.

Mindfulness-based stress reduction (MBSR) programs have been shown to enhance psychosocial and physical wellness (Proulx, 2003). Several studies have examined the use of MBSR in adolescents in various populations, but to date no study has been specifically designed for adolescents with Type 1 diabetes. In addition, several online programs and e-health systems have been utilized to enhance delivery of psychoeducation on diabetes management for adolescents with Type 1 diabetes (Wittemore, et al., 2013; Tercyak, Abraham, Graham, Wilson, & Walker, 2009).

Adolescence is often recognized as a particularly challenging time in the growth and development of youth even without the complication of a chronic disease. The existing research on adolescents with Type 1 diabetes focused on well-known issues of adolescence such as peer pressure and relationships with family (Bernstein, Stockwell, Gallagher, Rosenthal, & Soren, 2013; Helgeson, Escobar, Siminerio, & Becker, 2010). Few intervention studies have been conducted to date that have examined ways by which adolescents can reduce stress associated with the demands of diabetes management. Those that have, examined the effects of coping skills training (Grey, Boland, Davidson, Li, & Tamborlane, 2000); cognitive behavioral therapies (Perfect & Elkins, 2010); motivational enhancement therapy (Ismail, et. al., 2008) and multi-systemic therapy (Ellis, et.al., 2005).

MBSR programs have been used and applied with diverse populations and as an intervention, they are increasing in popularity. While the traditional MBSR course is structured with specific content and presentation, the intervention has been modified in content and length for adolescents (Kerrigan, et.al., 2011; Brown, et.al., 2011) and in delivery format such as online, web-based mindfulness training (Davis & Zautra, 2013). MBSR has been used and studied with the adolescent population. While it has been seen as an effective intervention for chronic illness and for adolescents, it has not been examined in the adolescent population with the chronic illness of Type 1 diabetes.

Engel's biopsychosocial model will be used to guide this study. The model has frequently been used to address treatment of those with cancer and diabetes because biological, psychological and social components of these chronic illnesses have been found to have a significant impact on effective disease management. Based on the autoimmune nature and difficult psychomotor demands of Type 1 diabetes management, this study with a focus on adolescents with this chronic autoimmune condition, has the potential to provide important data about the relationship between stress and effective disease management. The significance of this nursing research study is in the potential for improving the quality of life and management of diabetes by reducing the HbA1c of adolescents with Type 1 diabetes through the use of MBSR. The use of MBSR could provide a stress management technique for this population that would improve management of diabetes leading to significant reductions in both physiological complications associated with diabetes and psychological stressors associated with the management and care of diabetes in adolescents.

Data from this study will advance the science of nursing and provide a better understanding of the challenges faced by adolescents with Type 1 diabetes, as well as the importance of a comprehensive approach to health and wellness of patients, especially those with a chronic illness such as diabetes. Results of this study may provide diabetes health care professionals with evidence of a new and effective approach to improve care of adolescents with Type 1 diabetes. The specific aim of this study is to determine if a learned stress reduction method provided online will result in improvement of both psychosocial measurements of reported quality of life and physiological measurements of blood sugar control measured by HbA1c.

Research Design and Procedures

This study will utilize a between group repeated measures design to measure the effects of the learned MBSR intervention over time. MBSR will be the independent variable. Dependent variables include mindfulness, diabetic quality of life and HbA1c. Adolescents with Type 1 diabetes will be randomly assigned to an intervention group or a wait list/control group that will be offered MBSR after all data has been collected. The study will utilize a 2 (experimental versus wait-list control group) by 3 (pretest [Time 1], posttest [Time 2], and 3 month follow-up [Time 3]) to examine within and between group differences overtime on two psychosocial measures including mindfulness and quality of life. The physiological measure under study, HbA1c, reflects glucose control over the previous three month period and will be measured at Time 1 and Time 3. MBSR training will be provided via an online website and secure data collection site called *MySweetMind.org*.

Instruments

Two questionnaires will be used to collect data on psychosocial measures at the three time points including: 1) Diabetes Quality of Life Measure for Youths (YDQOL) (Ingersoll & Marrero, 1991) (Appendix A) and, 2) Mindful Attention and Awareness Scale for Adolescents (MAAS-A) (Brown, 2011) (Appendix B). A researcher-generated demographic sheet (DDS) (Appendix C) will also be administered at Time 1 to describe the population. These questionnaires will be administered to the participants via a secure, online data collection site in both the experimental and control groups. In addition, HbA1c will be measured at the beginning of the study (Time 1) to measure blood glucose over the previous three month period and after three months of participation in the study (Time 3) in participants in both the experimental and control group

Diabetes Quality of Life Measure for Youths (YDQOL) (Appendix A) will be used to measure adolescents on life satisfaction, diabetes impact, worries about diabetes, school life and peers. The YDQOL has a Cronbach alpha of 0.92 (Ingersoll & Marrero 1991). The YDQOL will take approximately 15 minutes to complete.

Mindful Attention and Awareness Scale for Adolescents (MAAS-A) (Appendix B) (Brown, 2011) will be used to measure the effectiveness of mindfulness training in youths and has been found to correlate with psychological well-being and healthy self-regulation. Cronbach's alpha varies from .82 to .84 in adolescent populations. The MAAS-A takes approximately 10 minutes to complete.

The Demographic Data Sheet (DDS) was researcher generated (Appendix C) and includes 11 questions about the participants. This information will be used to describe the population under study including age, gender, race, school grade and number of years with diabetes including date of diagnosis. Respondents will also be asked to describe their typical level of activity, if they wear an insulin pump or continuous glucose meter (CGM) and if they have sibling(s) and/or parent(s) with diabetes. The DDS will take less than 5 minutes to complete.

Glycated Hemoglobin test (HbA1c) (Appendix D) is a blood test requiring a venipuncture or finger stick. For this study, a finger stick will be self-obtained from each participant at Time 1 and Time 3. The instant HbA1c requires a drop of blood from the finger stick that provides results in 5 minutes. This measurement is useful because it is less affected by the day to day variations in blood glucose levels. The HbA1c is representative of average blood glucose over a 90 day period.

The HbA1c test kit will be sent to the home of the participant with simple instructions to place one drop of blood on the card provided. Parents or the adolescent participant will be asked to put the card into a reader that provides the results in the form of an electronic read out within 5 minutes. Those with Type 1 diabetes are familiar with this process as it is a common diagnostic test performed in the Endocrinologist's office at each visit. It is also the same type of finger stick procedure these adolescents use to test their blood sugar as they regularly do approximately 4-8 times per day. The parents will then be asked to e-mail this information to the researcher at Time 1 and Time 3. Reminder texts and e-mails (Appendix E) will be sent to the participants in both the experimental and control group. Reminders will also be posted on the website.

Sample Selection and Size

The population under study will include adolescents with Type 1 diabetes between the ages of 12 and 17. To participate, adolescents will need to have the ability to read English at a sixth grade level with no cognitive impairment and have access to a computer and the Internet. A power analysis was conducted using a medium effect size of 0.25, power of .80 with alpha set at .05 using a two tailed test of significance; thus, a total sample size (N) of 86 (n=43), per group will be needed.

Recruitment of Subjects

Recruitment fliers (Appendix F) will be posted at pediatric endocrinology offices in New Jersey. In addition, email invitations will be sent through the Diabetes Education and Camping Association (DECA). The primary recruitment method will be through direct promotion to parents and campers at two summer camps for adolescents with diabetes, one day camp and several other two-week/overnight camps. Information will be provided at intake and outtake days of the camp to the parents and campers. Both parents and camper will be given a postcard with the website address and general information about participating. Secondly, eleven Pediatric Endocrinology offices in New Jersey will be contacted in order to gain access to adolescent patients diagnosed with Type 1 diabetes. Physicians will be sent a letter (Appendix G) and asked to return an included post card if they are interested in having their patients participate in this study and if they are willing to help with recruitment including posting recruitment fliers and sending invitations (Appendix H) to adolescents and the parents of adolescents with Type 1 diabetes. Permission to recruit at these sites will be obtained. Additional recruitment activities will include word of mouth and announcements placed on the Internet via parent and child support groups.

Participants of this study will be able to participate in the privacy of their own home via a website for learning the MBSR program. Study participants will access the intervention through a developed website, *MySweetMind.org*. In addition, collection of all psychosocial data will occur via a secure online data collection site. HbA1c will be obtained via a self-collected finger-stick blood test at two specific time periods and the results will be sent by the participants' parents via email to the researcher for analysis.

Informed Consent Procedures

After obtaining approval from Duquesne University Institutional Review Board, recruitment activities will begin through the Diabetes Camp and several Pediatric Endocrinology offices.

Once a parent or adolescent contacts the investigator either by phone or e-mail, they will be screened via phone conversation for recruitment into the study by the researcher. Criteria for inclusion in the study is: (a) between the ages of 12 and 17; (b) ability to read English at a 6th grade level; (c) diagnosis of Type 1 diabetes; (d) no cognitive impairment as reported by parent; and (e) access to a computer and internet. Existing blood sugar control will not be used as inclusion or exclusion criteria. If the potential participant qualifies for the study, both adolescent and parent will be given the log in information.

The website will be accessible only through log in and is a private website; additional security was added by purchasing secure sockets layer (SSL) encryption for the website. A secure connection is created between the participant and the server which provides compliance with HIPPA regulations and confirms the security of the data. Potential participants and parents will be able to gain access to the content of the *MySweetMind.org* website through contact with the investigator once they obtain log in instructions via phone or e-mail.

Upon logging in to the website, the process of obtaining parental permission/consent and participant assent will begin. Once potential participants have had a chance to review the content and better understand the research study and what will be expected of them, they will have the opportunity to ask any additional questions online, via e-mail, or via telephone conversation with the researcher. Once all questions have been answered, assent and parental permission/consent forms will be sent via mail and returned via a prepaid envelope. Once obtained, participants and their parents will be given the online access code to the *MySweetMind.org* website. All assent forms and parental permission/consent forms will be stored in a locked cabinet in the PI's home office.

MBSR Online Intervention

The principles of MBSR will be divided into 6 main modules delivered in the online, web-based format via the website: *MySweetMind.org* (Appendix I). Participants will be given a password to access a 6 week module-based site to learn Mindfulness Based Stress Reduction adapted for adolescents. This adaptation of MBSR is based on the work of [name], FAAP and [name] as presented in the book (2015) written by [name], *The Mindful Teen*. The major topics included in each module are as follows: Module 1- Introduction to Mindfulness, Mindful Eating; Module 2 – Sitting Meditation; Module 3 – Body Scan; Module 4 – Mindfulness of Thinking & Everyday Mindfulness; Module 5 – Loving Kindness Meditation & Mindfulness Movement; and, Module 6 - Review & Tips for Maintaining a Mindfulness Practice. The key concepts for each module are shown in Appendix D. The website, *MySweetMind.org*, is currently under construction. The design will be user friendly, attractive and age appropriate. Each of the modules listed above will have short video vignettes (5-10 minutes) describing the content for current module. As the participant enters each module they will see images, hear music and voice descriptions which describe the mindfulness concept for that module. Also, the participant will see a written outline of the material that can easily be printed out, if the participant chooses to. In addition, suggestions for practice of the material will be given for each module. As the participant completes modules, they receive tokens representative of that completion which move forward as progress is made through the modules. The website is being designed to work on smaller devices such as phones and tablets as well as a computer.

Collection of Data and Method of Data Analysis

Upon initial access of the website, the participant will be asked to first complete the DDS, YDQOL and MAAS questionnaires delivered online and submitted online. In addition, the participants will be asked to test their HbA1c using a finger stick home testing kit that will be

sent via US mail to the parents of the adolescents who have agreed to participate. The parent of the participant will be asked to e-mail the results of the HbA1c to the PI.

Once all Time 1 data have been obtained, the participant will begin to go through the modules learning mindfulness. Within the website, the participant will be prompted to go to the diary page where the time spent on each module and time spent practicing the concepts of it will be recorded. This diary data will be accessible to the researcher. At the end of the 6 weeks allotted for the Module progression, the participants will be asked to take the YDQOL and the MAAS-A questionnaires again online. They will be encouraged to practice the mindfulness modules for 10-15 minute daily which will continue to be available. At Time 3, the participants in both the experimental and control groups will be asked to take the YDQOL and the MAAS-A questionnaires again one last time. The HbA1c test kit will also be sent to the home again and the results of this test will be emailed to the researcher. Those randomly assigned to the control group and thus, not yet had the opportunity to learn MBSR will be asked to take the YDQOL and MAAS-A questionnaires again at Time 2 and then the YDQOL and MAAS-A along with another HbA1c at Time 3. Once all data has been collected from those participants randomly assigned to the control group, participants will be offered the MBSR intervention.

Participants will be given a \$15.00 *iTunes or Amazon* gift card for completing the first three questionnaires and the HbA1c test at Time 1. The gift card will be sent via U.S. Mail upon confirmation of the receipt of the HbA1c results and completion of the questionnaires. At the end of the study, participants will be sent via U.S. Mail an additional \$25.00 *iTunes or Amazon* gift card upon receipt of the second HbA1c test results and completed questionnaires.

Procedures for the participants randomized to the control group will follow the same procedures as noted above except that they will not have access to the MBSR learning modules until the end of the three month data collection period. Those who were placed in the control group will be provided the opportunity to access the website and utilize the modules to learn mindfulness after all data have been collected and the intervention was shown to be effective in at least one variable measured.

Planned Analysis

Descriptive statistics will be used to describe the population under study including means, standard deviations, ranges, and percentages to summarize the information gathered on the demographic data sheet (DDS). Graphs and histograms will be generated to view demographic data and data collected on the major variables under study at Time 1 including mindfulness, diabetes quality of life and HbA1c. Assumptions for parametric testing will be tested to determine whether or not parametric testing can be done. Although parametric testing is planned, it may be that the equivalent nonparametric test will be used to analyze data. In addition, a correlational matrix will be created to determine whether any two variables co-vary at > 0.65 . Two way repeated measures Analysis of Variance (RM-ANOVA) will be used to answer the research questions.

Interactions with Subjects and Subjects' rights

In the development of this study, careful consideration was given to maintain the 7 principles as outlined within the NIH document concerning treatment of research subjects. Specific to the

interactions with subjects, a fair subject selection will be utilized, IRB approval and informed consent will be obtained. Additionally, respect for enrolled subjects will be demonstrated by checking on their well-being as they participate, maintaining confidentiality and sharing results with them once the study is complete. Those subjects who are in the control group will also be given the opportunity to learn MBSR at the completion of data gathering since it has been shown in many populations to be a benefit and advantage to individuals with varied health conditions.

All information gathered including data, parental permission/consent and assent forms will be stored in a locked cabinet with careful attention to the privacy of participants and security of all materials. The website will be accessible only through log in and is a private website; additional security was added by purchasing secure sockets layer (SSL) encryption for the website. A secure connection is created between the participant and the server which provides compliance with HIPPA regulations and confirms the security of the data. Only the researcher and advisor will have access to the data collected.

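### Is Time 3 dated inconsistently: three months after the posttest, or three months after entry?

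*Protocol*

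**What the plan says.** Under Research Design and Procedures, the 2 by 3 layout for mindfulness and quality of life is "pretest [Time 1], posttest [Time 2], and 3 month follow-up [Time 3". No starting point is attached to the three months. The same paragraph says HbA1c is taken at Time 1 and Time 3.

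Under Instruments, one sentence places the first HbA1c at the beginning of the study, named as Time 1, and the second "after three months of participation in the study (Time 3". The same section states: "The HbA1c is representative of average blood glucose over a 90 day period".

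Under Collection of Data and Method of Data Analysis:

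- Start of modules: "Once all Time 1 data have been obtained, the participant will begin to go through the modules learning mindfulness".
- Time 2 questionnaires: "At the end of the 6 weeks allotted for the Module progression".
- Time 3 questionnaires: "At Time 3, the participants in both the experimental and control groups will be asked to take the YDQOL" and the MAAS-A for the last time, with the HbA1c kit mailed again. No week is given.
- Control group: same procedures, except that "they will not have access to the MBSR learning modules until the end of the three month data collection period".

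**The concern.** In a pretest, posttest and follow-up sequence, a three-month follow-up is normally counted from the posttest. With the posttest at week 6, that gives about week 19. The Instruments section and the control-group paragraph point to about week 13. If both readings were live, the final mindfulness and quality-of-life scores could mean durability three months after training, or status about 7 weeks after it. The Time 3 HbA1c, with its 90-day look-back, could cover mostly the study period from Time 1 or only time after the modules.

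Two further points add to the doubt. The label sits in the sentence about the psychosocial measures while the anchored phrase is about HbA1c, so the two might be collected on different dates under one name. And modules start only once Time 1 data are in, which depends on a mailed kit and an e-mailed result, so week 13 is itself approximate.

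**Working it through.** **The plan's own figure.** The only computed figure is N = 86 (Sample Selection and Size: effect size 0.25, power 0.80, two-tailed alpha 0.05). For the between-group test in a repeated measures ANOVA with 2 groups and m = 3 assessments, the noncentrality is N × f² × m / (1 + (m − 1) × rho). The protocol gives no rho. Assuming rho = 0.5, this is 86 × 0.0625 × 3 / 2 = 8.06, with power 0.801, so 86 reproduces. Under rho = 0.3 or 0.7 the required N would be 70 or 104. The date of Time 3 does not enter the formula, so N is the same on either reading.

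**The calendar.** Three months = 3 × 365.25 / 12 / 7 = 13.04 weeks. The posttest is at week 6.

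| | From posttest | From Time 1 |
|---|---|---|
| Time 3 | 6 + 13.04 = week 19.0 | week 13.0 |
| Gap after posttest | 13.0 weeks | 13.04 − 6 = 7.0 weeks |
| Length of data collection | 19.04 / 4.348 = 4.4 months | 3 months |
| 90-day (12.86-week) HbA1c window | weeks 6.2 to 19.0 | weeks 0.2 to 13.0 |

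**Which reading the text supports.**

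1. No passage says that Time 3 is three months after the posttest or after the modules. Week 19 comes only from the customary sense of a label.
2. The Instruments sentence names both ends: the beginning of the study is Time 1, and Time 3 follows three months of participation. The natural origin is Time 1.
3. The control group waits "until the end of the three month data collection period" and is offered the modules after all its data are in. A week-19 assessment would fall about 1.4 months (4.4 − 3) beyond that period.
4. The questionnaires and HbA1c are one occasion. The data collection section puts the last questionnaires and the second kit together at Time 3, and lists them together for controls. Splitting them across weeks 13 and 19 would contradict that section.

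Points 2 and 3 agree with each other and exclude week 19. The label is also compatible with three months from baseline, so one reading makes every passage consistent.

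**Delay before the modules.** Take Time 3 at day 91 from entry and 42 training days. If modules start d days after entry, the gap from posttest to Time 3 is (91 − 42 − d) / 7 weeks: 7 for d = 0, and 6, 5 or 4 for d = 7, 14 or 21. These delays are assumptions. Controls complete the same Time 1 procedures, so the delay in completing Time 1 arises in both groups.

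A further calculation of how much of a glucose effect HbA1c would show at week 13 needs an onset pattern, a start delay and daily weights, none of which the protocol gives. It would address HbA1c lag, not the date of Time 3.

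**The case for a change.** The strongest case for a change is that no passage gives Time 3 in weeks, with an origin and a window, and that timing of tests, kit mailing and control access are protocol matters. Time 3 is the last value for every outcome and the sole post-baseline HbA1c. At week 13 the HbA1c window takes in the training weeks; at week 19 it lies wholly after them. These are different quantities, and a week-13 result reported as a three-month follow-up could mislead. An origin at module start would not exist for controls. The remedy would be a matter of wording.

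Part of this stands. The label is loose, and Time 3 results should be described as roughly 7 weeks after the end of the modules. The rest does not require a change:

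- The research questions and the stated aim ask whether the programme improves mindfulness, quality of life and HbA1c relative to control. Neither promises an effect three months after training.
- A three-month interval from Time 1 matches the protocol's own HbA1c look-back, and participants are encouraged to keep practising after week 6. The Time 3 HbA1c therefore reflects the study period, which is a reasonable choice.
- Visit windows and exact day counts are commonly left to the SAP, which is not at hand.
- The origin is available to both groups, because the Instruments sentence ties it to Time 1.

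**Conclusion.** The concern does not call for a change. The week-19 reading, 6 weeks later than the supported one, depends on taking an unanchored label in its customary sense against two agreeing statements in the same document. Read as a whole, the protocol puts Time 3 about three months after Time 1, near week 13 and about 7 weeks after the posttest. That gap shortens to 4 to 6 weeks only if three months is counted from entry and modules start 1 to 3 weeks later, which is an assumption.

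On that reading both groups are assessed at the same Time 3, so the randomised comparison is not biased, and N = 86 does not depend on the date. Dating the label would tidy the text without altering any result. An analyst or author working from the Instruments section and the actual assessment dates would describe Time 3 correctly. This conclusion assumes that participation begins at Time 1, as the Instruments sentence implies, and that questionnaires and HbA1c are collected together at Time 3, as the data collection section says.

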Appendix G

Sample Pediatric Endocrinologist Recruitment Letter

April 1, 2015

[name]
Pediatric Endocrinology

Dear [name],

This letter is to request the participation of your office in research concerning the use of Mindfulness as a stress management technique for adolescents with Type 1 diabetes.

I am conducting this study as partial fulfillment of the requirements for the PhD degree in Nursing at Duquesne University. IRB approval to conduct this study has been obtained through Duquesne University.

I am asking for your help to recruit adolescents between the ages of 12 to 17 with Type 1 diabetes to participate in this study. Participants will be randomized to the experimental group or the waitlist/control group. If interested, the participants will be invited to learn the practice of mindfulness via modules on a website, asked to practice the MBSR techniques, and asked to respond to questionnaires via a secure online data collection site. The home page of the website where your patient will access the course material is www.mysweetmind.org.

If you agree to help me recruit, business cards and postcards will be provided to you to give to your patients and their parents that will contain information about the study. If your patients are interested, they will be asked to contact me directly. Participants would be under no obligation to join the study or continue in the study once they join.

Please complete and send via U.S. Mail the enclosed pre-stamped postcard if you permit this study to be advertised in your office. I am available to meet with you and/or your staff directly to describe the study further or answer any questions you may have.

I encourage you to consider this opportunity for your patients. Mindfulness has become quite popular in the last few years and has shown significant benefits for many different individuals with varying conditions/illnesses. The skills that your patient could gain have the potential for helping them for a lifetime.

Please do not hesitate to contact me with any questions. My cell phone number is [contact]

Sincerely,

[name], MSN, RN, CNE
PhD Candidate
Duquesne University
School of Nursing

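### Do the conflicting statements on control-group access to the modules call for a change to the plan?

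*Protocol*

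**What the plan says.** Four places in the protocol bear directly on when the control group may use the modules.

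- Research Design and Procedures describes a "wait list/control group that will be offered MBSR after all data has been collected".
- Collection of Data and Method of Data Analysis, in the paragraph on the three time points, says: "Once all data has been collected from those participants randomly assigned to the control group, participants will be offered the MBSR intervention".
- The last paragraph of that section first says of controls that "they will not have access to the MBSR learning modules until the end of the three month data collection period". It then closes with access coming "after all data have been collected and the intervention was shown to be effective in at least one variable measured".
- Interactions with Subjects and Subjects' rights says: "Those subjects who are in the control group will also be given the opportunity to learn MBSR at the completion of data gathering". The reason given is "since it has been shown in many populations to be a benefit and advantage".

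The physician letter in Appendix G mentions the "waitlist/control group. If interested, the participants will be invited to learn the practice of mindfulness via modules on a website". It says nothing about when controls get access or on what condition.

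The outcomes are mindfulness (MAAS-A), diabetes quality of life (YDQOL) and HbA1c. The planned size is 43 per group, 86 in total, with a two-tailed alpha of .05 (Sample Selection and Size).

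**The concern.** The closing sentence on access joins two requirements with the word and: data collection is over, and the trial has shown an effect. The other statements that offer the modules set only the first requirement. After a null result an investigator could not satisfy both readings, and a statistical analysis plan would not normally settle what adolescents and their parents are promised.

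The sentence also looks troubling to a statistician. It is the one place where the protocol says what being effective would amount to, and it asks for success on any one of three unranked outcomes. Read as a criterion for the trial, it would let a single chance result carry the conclusion. The stakes would then be an inflated false-positive rate as well as an unclear promise to controls.

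**Working it through.** The protocol states no figure on this point, so the check is mainly a comparison of texts.

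**Step 1. What each statement requires.**

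| Place | Data collection over | Effect shown in this trial |
|---|---|---|
| Research Design and Procedures | yes | not required |
| Collection of Data, paragraph on time points | yes (control-group data) | not required |
| Collection of Data, last paragraph, next-to-last sentence | yes (a restriction only) | not mentioned |
| Collection of Data, last paragraph, last sentence | yes | required |
| Subjects' rights | yes | not required; rests on evidence from other populations |

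**Step 2. When the statements disagree.** If an effect is shown, all of them give access. They differ at most in whether the analysis must be finished first, and this difference is slight, because a promise of access after data collection sets an earliest date and no deadline. If no effect is shown, the last sentence withholds the modules and the others offer them. The people affected are the 43 planned controls.

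**Step 3. Whether either reading touches the data.** Each participant supplies two questionnaires at three time points and HbA1c at two: 2 × 3 + 1 × 2 = 8 outcome measurements, the last of them at Time 3. Under every statement in the table, access for controls comes after Time 3. The number of outcome measurements taken after access is therefore 0 under either reading. The between-group comparison, its standard error, the power and the alpha are the same whichever sentence prevails.

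**Step 4. The one-variable phrase as an efficacy rule.** Suppose, as an assumption, that it were used that way, with one unadjusted test on each of three independent outcomes and no true effect.

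- Either direction counts, two-tailed .05: 1 − 0.95³ = 1 − 0.8574 = 0.1426, about 14%.
- Benefit only, .025 each: 1 − 0.975³ = 1 − 0.9269 = 0.0731, about 7%.
- With an assumed correlation of .8 between the test statistics, the same quantities fall to 0.0982 and 0.0491.

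These figures describe a rule that the protocol does not adopt. They also do not fit the named test. Planned Analysis specifies a two-way repeated measures ANOVA. For the two questionnaires, a group-by-time test over three time points has (2 − 1) × (3 − 1) = 2 numerator degrees of freedom and no direction, so a benefit-only rate built from single z-tests does not describe it. The figures therefore do not measure the size of any defect here.

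**The case for a change.** The strongest case for a change is that the contradiction is certain, concerns a commitment to minors, and would cost only a few words to remove. It cannot be explained away by calling the shorter statements shorthand for the longer one. The section on subjects' rights bases the offer on benefit in other populations, and an offer justified in that way does not wait on this trial's result. All of this stands.

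Three parts of the case do not carry the same weight.

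- The letter in Appendix G is a general description for physicians. It makes no statement about control access that would need reconciling.
- The protocol is not silent on how effects will be judged. Research Questions gives the direction and the comparison ("increase mindfulness and improve quality of life in adolescents with Type 1 diabetes compared to a control group"), Sample Selection and Size gives the alpha, and Planned Analysis names the test. The access sentence merely does not repeat them.
- Naming a primary outcome and handling multiplicity are commonly left to a statistical analysis plan. None is shown here, so their absence cannot be held against a sentence about website access.

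There is one indirect route to the data. What controls were told about later access could affect how many stay in the study or how they answer questionnaires. The consent pages are not shown, so nothing in the document supports or excludes this, and it cannot be made a finding.

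**Conclusion.** The wording conflict is real but narrow. It arises only after a null result and concerns what the 43 planned controls may use once the study is over. Its effect on the trial's estimates, power, error rates and conclusions is nil, because every version puts access after the last outcome measurement.

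This rests on two assumptions: that controls are in fact kept from the modules until Time 3, as every version says, and that the one-variable phrase is used only for access, as the text has it. On that basis no change to the design or analysis plan follows. The sentences should be brought into agreement with each other, and with the consent text, as an editorial matter. Which access rule should stand is for the sponsor and the ethics board to decide.
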